Study Protocol and Statistical Analysis Plan

Title: Effects of an exercise program for people with diabetic foot ulcers: A feasibility study with outcomes

Registration number: NCT03002155

Document date: Updated 2022-07-07

Aim of study:

This research aimed to address the concerning cycle of deconditioning and disablement in people with DFUs by introducing a seated exercise intervention to improve meaningful health and quality of life outcomes. We examined the feasibility of conducting a randomized controlled trial to assess the effects of 12-weeks of seated exercise in people with DFUs compared to peers who did not exercise. We also assessed physical, physiological, and psychosocial health outcomes in both groups. The exercise intervention in this study was EnhanceFitness,¹ an community-based group exercise program appropriate for people with weight-bearing restrictions due to wound-healing protocols. Numerous studies have been conducted that provide evidence of health benefits associated with participation in EnhanceFitness in older adults, including participants with diabetes.²⁻⁷ We hypothesized that people with DFU who engaged in the fitness program would report high levels of satisfaction, adherence and participation, and a low frequency of adverse events. We also hypothesized that participation in the exercise program would be associated with improvements in key health outcomes as compared to a standard-care control group, who were instructed not to engage in regular exercise (i.e., not to change their current habit of no regular exercise).

Materials and methods

A pilot randomized controlled trial was conducted. Study participants were randomly assigned to a group-based exercise program with a seated option for participation (the EnhanceFitness intervention, described below) or to the control group. Participants in the exercise group attended fitness classes for a 12-week period; those in the control group received standard care, which did

not include exercise. Both groups of participants were assessed at two time points, baseline and 12-week follow-up.

Participants

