Feasibility Outcomes. We assessed feasibility outcomes to inform future, large-scale RCT research in this area. The feasibility of conducting a RCT to assess effects of seated exercise in people with DFUs was evaluated using the following parameters: (1) recruitment and retention; (2) adherence to the exercise protocol; (3) participant satisfaction with the exercise program; and (4) presence of serious adverse events. Retention was quantified as the percent of participants that completed the study (i.e., attended both the baseline and 12-week follow up appointments), as well as percent of those who withdrew during the study or were lost to follow-up in each arm. Adherence was quantified as percent of exercise sessions attended by those randomized to the exercise group (out of 36 possible sessions). Satisfaction with EnhanceFitness was quantified as a continuous score on a measure of satisfaction, ranging from 0 (not at all satisfied) to 5 (very satisfied). Finally, presence of serious adverse events (SAEs: adverse outcomes, related or unrelated to the study, such as hospitalizations, emergency room visits, increase in wound size,

and infection, over the course of the study) was quantified as the total number of SAEs reported by participants in each trial arm.

Health Outcomes. We anticipated that exercise might affect many aspects of health and health-related quality of life in people with current or recently-healed DFUs. The following health outcomes were assessed: (1) glycated hemoglobin (HbA1c¹⁰); Five-times sit-to-stand test (5xSTS, a measure of lower extremity strength¹¹); Timed-up-and-go (TUG, a measure of functional mobility¹²); and 30-second biceps curls (a measure of upper extremity strength). We also asked participants to complete a survey comprised of standardized self-reported health measures, including the Patient-reported Outcome Measurement Information System measures of global health (PROMIS-Global 10-item short form),¹³ depression (PROMIS-Depression 4-item short form),¹⁴ fatigue (PROMIS-Fatigue 8-item short form), and physical function (PROMIS-Physical Function 11-item short form).¹⁵ The Activities-Specific Balance Confidence Scale was used to assess balance confidence.¹⁶

Additional variables. Participant characteristics (e.g., age, sex, body-mass index, duration of diabetes) were collected at baseline to characterize the sample and evaluate the comparability between the exercise and control groups.

Procedures

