12-week data collection session. At the 12-week session, we administered a follow-up survey to assess changes in the previously listed self-reported health outcomes. The survey also included questions to assess satisfaction with the EnhanceFitness intervention for participants in the exercise group. Following the survey, we asked participants to perform the 5xSTS, TUG, and biceps curls. At the end of the session, the participant returned to the laboratory to have their blood drawn and tested for HbA1c.

Analysis

Sample Characteristics. Descriptive statistics (mean, standard deviation, frequency distributions) were calculated for variables used to characterize the sample (e.g., participant characteristics). Student *t*-tests (numeric data) and Chi-square tests (nominal data) were used to compare the intervention and control groups based on participant characteristics. The alpha level for these tests was set at $\alpha=0.05$ and significant findings for sample variables indicate that there are differences in demographic or clinical characteristics (e.g., age, sex, duration of diabetes) between the exercise and control groups.

Feasibility Outcomes. The ability to meet recruitment targets (20 participants per group, 40 total) was assessed. Retention (or percent of participants that completed the study) and percent attrition was calculated and reported separately for the intervention and control groups. Pre-intervention

characteristics were compared between participants who did and did not complete the study to determine if there was a biasing effect. Adherence to the protocol was assessed in the intervention group to quantify the extent to which participants attended exercise classes. Satisfaction with EnhanceFitness was assessed in the intervention group to ensure that participants reported a minimum of 4 on a 5-scale measure of satisfaction with the exercise intervention.

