Health Outcomes. Descriptive statistics were calculated for all physical, physiological, and psychosocial outcomes. Separate repeated measures analyses of variance (ANOVA) were performed for each health outcome. The ANOVA models included two factors, each with two levels (group: intervention, control; time: pre-intervention, post-intervention). The alpha level was set at $\alpha=0.10$ for health outcomes and was not adjusted for multiple comparisons. A less conservative statistical approach is warranted for this pilot study so that effects of the intervention could be recognized and, if results suggested that the intervention was beneficial, the results could be used to power and inform a larger RCT. Significant interactions of group x time (with corresponding evidence of improved outcomes in the intervention group) would indicate that the exercise program improved physical, physiological, and psychosocial outcomes in the exercise group compared to the control group.

References

8. Dugan JA. Exercise recommendations for patients with type 2 diabetes. *Jaapa*. 2016;29(1):13-8.

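### At least nine health outcomes are tested at a lenient, unadjusted pilot threshold, yet significance is allowed to show that exercise improved them, with nothing marking the finding as preliminary

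*Combined protocol and SAP*

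**What the plan says.** The list introduced by "The following health outcomes were assessed" (Outcomes, Health Outcomes), with the survey measures that follow it, holds nine instruments:

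- one laboratory measure (HbA1c);
- three performance tests (5xSTS, TUG, biceps curls);
- four PROMIS short forms (Global, Depression, Fatigue, Physical Function);
- the balance confidence scale.

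None is marked as primary. The Aim of study hypothesizes that "participation in the exercise program would be associated with improvements in key health outcomes" but does not say which outcomes are the key ones.

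On the tests, Analysis, Health Outcomes states: "Separate repeated measures analyses of variance (ANOVA) were performed for each health outcome". The alpha level is 0.10 "for health outcomes and was not adjusted for multiple comparisons". The reason follows: "A less conservative statistical approach is warranted for this pilot study so that effects of the intervention could be recognized". The same sentence goes on to name the intended use of the findings: "if results suggested that the intervention was beneficial, the results could be used to power and inform a larger RCT".

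The section then closes with the rule for reading the results: "Significant interactions of group x time (with corresponding evidence of improved outcomes in the intervention group) would indicate that the exercise program improved" the physical, physiological and psychosocial outcomes of the exercise group compared with control.

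**The concern.** Two adjacent sentences do not match. The first justifies a lenient threshold because the study is a pilot that looks for effects worth taking into a larger trial. The second attaches to that threshold a causal, comparative conclusion: the program improved the outcomes. Nothing in that sentence, or elsewhere in the document, says that the conclusion is preliminary or awaits confirmation.

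The Aim of study makes better health outcomes than control a study hypothesis, so this is the sentence by which that hypothesis would be judged. Followed as written, the report could state that seated exercise improved a health outcome in people with diabetic foot ulcers, on evidence that supports only a signal for further study. The rule also leaves open how many outcomes must be significant, and what counts as the corresponding evidence of improvement named in its bracket.

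**Working it through.** The plan gives no power calculation and no overall error rate, so there is no stated figure to reproduce. The check asks how often the rule would yield a false-benefit result if the arms did not differ.

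**Inputs from the document**
- Alpha: 0.10 per outcome, unadjusted (Analysis, Health Outcomes).
- Number of outcomes: 4 laboratory and performance measures + 4 PROMIS forms + 1 balance scale = 9 (Outcomes, Health Outcomes). This counts instruments. The plan does not say whether PROMIS-Global is scored once or as separate physical and mental summaries; two scores would make 10. Hence at least nine.
- Group size: 20 per arm, from "The ability to meet recruitment targets (20 participants per group, 40 total) was assessed" (Analysis, Feasibility Outcomes).

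**Assumption not in the document**
- Correlation between outcomes: none is given, so a range is shown.

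**Step 1: one outcome.** With two groups and two time points, the group x time interaction is equivalent to a two-sample t-test on change scores. The F test is non-directional, and the bracketed condition keeps only results that favour exercise:

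0.10 / 2 = 0.05.

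This is an upper value. If the bracket asks for more than a between-group difference favouring exercise, the qualifying results are a subset and the rate is lower. How much lower depends on how both arms change over 12 weeks, which the plan does not give.

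**Step 2: expected number among nine.** Expectations add whatever the correlation:

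9 x 0.05 = 0.45 (with ten scores, 10 x 0.05 = 0.50).

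**Step 3: at least one of nine, if one positive were enough.** For independent outcomes:

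1 - 0.95^9 = 1 - 0.630 = 0.370 (with ten scores, 1 - 0.95^10 = 0.401).

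For correlated outcomes this was simulated: 20 per arm, no group difference, nine outcomes with equal pairwise correlation, t-test on change scores, 100,000 runs per value.

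| Assumed correlation | At least one false-benefit result |
|---|---|
| 0 | 37% |
| 0.3 | 29% |
| 0.5 | 24% |
| 0.7 | 18% |

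Steps 1 and 2 need no correlation assumption. Step 3 needs both a correlation and the reading that one positive suffices.

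**The case against.** The strongest reply is that this is a matter of tone. The title calls the work a feasibility study, the feasibility outcomes come first, and the hypothesis speaks of association. The lenient alpha and the lack of adjustment are disclosed and explained in the sentence just before the one at issue. An unranked set of exploratory outcomes is normal in a pilot. Read in place, the closing sentence may only explain how a significant interaction is interpreted. It is also plural, so it does not say that one positive result is enough.

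Much of this stands. The threshold is acceptable, the absence of a primary health outcome is not a fault in itself, and the point concerns wording. What does not stand is that the context supplies the missing caution. The closing sentence is the one that tells the report what significance means, and it carries no qualification.

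A reader might infer more than the document supports:

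- **That alpha 0.10 or the lack of adjustment is an error.** The plan gives a reason that suits a pilot.
- **That 37% is the trial's false-positive rate.** That figure needs independent outcomes and a one-positive rule; the plan states neither.
- **That a definite lower rate applies**, because the bracket demands improvement within the exercise arm or because positives are needed in each type of outcome. The first depends on change over time in both arms; the second on a grouping of the measures that the plan does not provide.
- **That inflated pilot effects will be used to size the next trial.** The plan does not say which results would be used.

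**Conclusion.** The concern holds in a limited form: the conclusion rule for the health outcomes is stronger than the rationale given for the threshold behind it. With no true group difference, the size is up to 5% per outcome and up to about 0.45 false-benefit results expected among nine, with no assumption about correlation. The figures for at least one false benefit (37% if independent, about 18% to 29% at assumed correlations of 0.7 to 0.3) are conditional on one positive being taken as enough, and should be cited only with that condition. The calculations treat the nine instruments as nine tests and rest on the usual assumptions of the t-test.

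This is a cheap improvement, not a flaw in the design or in the tests. It affects what the report may conclude.

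**What to change.** Keep alpha 0.10. Replace the last sentence of Analysis, Health Outcomes with:

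> For every health outcome we report the between-group difference in change with its 90% CI. These analyses are exploratory; an unadjusted p<0.10 with a between-group difference favouring exercise is a signal for further study and does not by itself show that the program improved the outcome.

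This brings the conclusion into line with the plan's own rationale. It also settles the bracketed condition, by defining a favourable result as a between-group difference, and removes the need to fix how many positives would count.

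The cost is two sentences in the plan and matching wording in the report, with no extra participants, data or tests. The document is written in the past tense, so only the reporting changes. The downside is that the reported claims become less favourable.
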